6.7 STANDARD OF CARE FOR DIABETIC LOWER LIMB ULCERS

Standard care will be documented in CRF including the type of care (e.g., extent of debridement, use of concomitant medications), timing, and frequency. Parameters for consideration in choosing standard care procedures for diabetic lower limb ulcer include, but not limited, the following:

- Debridement: Removal of necrotic or infected tissue. During TWB-103 treatment period, if judged by the investigator as appropriate, lesser wound debridement is allowed. However, if major surgery is required, the subject should be withdrawn from this study.
- Off-loading: During study period, off-loading devices, such as clutches, wheel chair, off-loading

shoes, etc., may be applied as judged by Investigator.

- Revascularization or other treatment to improve circulation. However, revascularization is prohibited during treatment period (Visit 2~Visit 13).
- Maintenance of a moist wound environment.
- Management of wound infection: If the target wound has low grade infection (\leq Grade 2) during TWB-103 treatment, whether to stop TWB-103 treatment will be judged by the investigator and appropriate treatment to control the infection will be provided at the investigator's discretion. However, if wound is infected ($>$ Grade 2) during TWB-103 treatment or the treatment for the ulcer wound infection requires subject's hospitalization, intravenous infusion or muscular injection of antibiotics, TWB-103 treatment must stop and be replaced by appropriate treatment to control the infection.
- Wound cleansing
- Good blood glucose control: Considering each subject's physical and physiological condition, "good blood glucose control" is defined as blood glucose level as good as possible with the help of physicians. Subjects will have appropriate medication and education to control the blood glucose level. The investigator will also monitor subjects' blood glucose level through the laboratory tests, including fasting glucose and HbA1c test results, collected during this study.

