7 STUDY INTERVENTION DISCONTINUATION AND SUBJECT WITHDRAWAL

7.1 STUDY INTERVENTION DISCONTINUATION

If the target wound has low grade infection (\leq Grade 2) during TWB-103 treatment, TWB-103 treatment may continue or discontinue as judged by the investigator and appropriate treatment to control the infection will be provided at the investigator's discretion. However, any subject with $>$ Grade 2 skin infection in the ulcer wound, or the treatment for the ulcer wound infection requires subject's hospitalization, intravenous infusion or muscular injection of antibiotics, must not receive any further TWB-103 treatment.

If allergy is judged as likely due to the investigational product, it is dangerous to continue using the investigational product. Therefore, any subject who experiences \geq Grade 1 allergic reaction at least possibly related to the investigational product (section 8.4.3.2) must stop TWB-103 immediately.

During TWB-103 treatment period, if judged by the investigator as appropriate, lesser wound debridement is allowed. However, if major surgery is required, the subject should stop TWB-103 treatment.

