7.2 SUBJECT WITHDRAWAL FROM THE STUDY

A subject may withdraw voluntarily or involuntarily from the trial due to any of the following conditions:

1. The subject voluntarily decides to withdraw her/his consent.
2. The subject's pregnancy is confirmed after enrollment till last dose of TWB-103.
3. The subject received or plans to receive any prohibited therapy as defined in section 6.6.
4. The subject dies or is lost to follow-up.
5. Any pathological event, clinical adverse event, laboratory abnormality, intercurrent illness, or any occurrence or change in the subject's status giving indication to the investigator that further participation in the study may not be the best interest of the subject.
6. The subject develops $>$ Grade 2 skin infection in the ulcer wound, or the treatment for the ulcer wound infection requires subject's hospitalization, intravenous infusion or muscular injection of antibiotics.
7. The subject experiences \geq Grade 1 allergic reaction at least possibly related to the investigational product (section 8.4.3.2).
8. The subject requires a major surgery debridement.

9. The study is terminated prematurely by the investigator, research institution, sponsor, IRB/IEC or regulatory authorities.

If the withdrawal is decided during TWB-103 treatment period, the withdrawn subject will be encouraged to complete the assessments of Week 12, within 1 week of the withdrawal decision, as End of Study (EOS) visit before exiting from the study. Laboratory, pregnancy and PRA tests done within 1 week prior to EOS visit are acceptable.

If the withdrawal is decided in the follow-up period, the withdrawn subject will be encouraged to complete the assessments of Week 36, within 2 weeks of the withdrawal decision, as EOS visit before exiting from the study.

The reason for withdrawal must be recorded. If a subject is withdrawn due to an AE, every effort will be made to follow the event until event resolves or stabilizes at a level acceptable to the investigator.

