9.4 STATISTICAL ANALYSES

9.4.1 GENERAL APPROACH

There will be a separate formal statistical analysis plan (SAP) to be completed prior to database/data lock. The SAP generally includes additional statistical analysis detail (e.g., more detail of analysis populations, summary of statistical strategies). Any deviations from the planned analysis as described in the SAP will be justified and recorded in the final clinical study report.

The baseline value of each assessment will be the value assessed closest and prior to 1st application of TWB-103.

Descriptive statistics will be provided for all endpoints.

Continuous variables will be summarized by reporting the number of observations, mean, standard deviation, median, interquartile range (IQR = third quartile (Q3) - first quartile (Q1)), Q1, Q3, minimum and maximum.

Categorical variables will be summarized using frequency tables showing the number and percentage of subjects within a particular category.

Ordinal endpoints will be presented by transition tables.

Healing time from baseline to wound closure will be estimated by using Kaplan-Meier method.

The data changes from baseline value will be analyzed by one-sample t-test or Wilcoxon sign rank test. The baseline value of each assessment will be the value assessed closest and prior to 1st application of TWB-103. The Last Observation Carried Forward (LOCF) method will be applied for dealing missing data of the efficacy endpoints.

All comparisons will be conducted with significance level of 0.05, using 2-tailed tests where 95% confidence interval for difference and corresponding *p*-value will be presented.

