9.4.3 ANALYSIS OF THE SECONDARY ENDPOINTS

For changes of wound area and (if data available) wound volume measured by 3D camera from the baseline values, data will be analyzed by using one-sample t-test or Wilcoxon sign rank test on ITT and PP population.

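### LOCF can carry wound shrinkage measured before a wound-related failure to Week 12, which biases the ITT mean area and volume reduction upward

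*Combined protocol and SAP*

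**What the plan says.** Section 9.4.1 states: "The Last Observation Carried Forward (LOCF) method will be applied for dealing missing data of the efficacy endpoints". It makes no exception by endpoint or by reason for missingness. It defers further detail to a separate formal SAP, which is not among the documents.

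Section 7.2 lists the grounds on which a subject may leave the trial. Three bear directly on the wound or its treatment:
- Item 6: skin infection of the ulcer above Grade 2, "or the treatment for the ulcer wound infection requires subject's hospitalization, intravenous infusion or muscular injection of antibiotics".
- Item 8: "The subject requires a major surgery debridement".
- Item 3: "The subject received or plans to receive any prohibited therapy as defined in section 6.6". Section 6.6 counts intravenous and intramuscular antibiotics during the treatment period as prohibited.

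For a withdrawal during treatment, section 7.2 says that "the withdrawn subject will be encouraged to complete the assessments of Week 12, within 1 week of the withdrawal decision". Section 4.4 treats a subject who withdraws during treatment and attends that visit as having completed the study, so no later area is expected.

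Section 9.3 keeps every treated subject with any post-treatment evaluation in ITT. Section 9.4.3 sets the tests, "For changes of wound area and (if data available) wound volume measured by 3D camera from the baseline values": a one-sample t-test or Wilcoxon signed rank test in ITT and PP. Section 9.4.1 adds two-sided testing at 0.05, with p-values and 95% confidence intervals.

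**The concern.** The withdrawal list ties some of the missing data to deterioration of the wound being measured. LOCF assumes that the last area stands for the later ones. That is least credible for a subject who left because the wound became seriously infected or needed major surgery.

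Suppose the wound had shrunk by a third at one weekly visit and the subject was withdrawn for infection before the next, without an exit assessment. The analysis would enter a one-third reduction for that subject at every remaining week to Week 12. If a post-failure area is recorded instead, the same clinical course enters as enlargement. The score then depends on a visit that is not required.

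With about 10 ITT subjects, one or two such values can move the mean, the confidence interval and the p-value. Those are what the reader will see for area and volume, and efficacy is the only secondary objective.

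**Working it through.** **The plan's own figure.** Section 9.2 plans 10 subjects to obtain 8 evaluable ones, a gap of 10 − 8 = 2. An allowance of 20% gives 8/(1 − 0.20) = 10, but the documents state no dropout rate, and 15% also rounds up to 10 (8/0.85 = 9.4). The documents do not say why subjects would be non-evaluable. Two failures is therefore a convenient case, not a planned one.

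**Illustration 1: mean percent reduction at Week 12.** The documents give no expected reduction, SD or failure rate, so these inputs are assumptions: n = 10; completers at 60%; failures at 35% before failure and −20% (enlargement) after it. With f failures each scored v:

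mean = [(10 − f) × 60 + f × v] / 10

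| f | LOCF, pre-failure area carried (v = 35) | Scored no reduction (v = 0) | Post-failure area recorded (v = −20) |
|---|---|---|---|
| 1 | 57.5 | 54 | 52 |
| 2 | 55 | 48 | 44 |
| 3 | 52.5 | 42 | 36 |

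For f = 2: (480 + 70)/10 = 55; 480/10 = 48; (480 − 40)/10 = 44. The difference between all failures skipping the exit visit and all attending is 5.5, 11 and 16.5 points for f = 1, 2 and 3.

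**Illustration 2: varying the carried value.** Let L be the last percent reduction and T the score under a failure rule. The shift in the mean caused by LOCF is (f/10) × (L − T). T = −30 borrows the 30% enlargement that section 8.4.1 requires to be reported as an AE. For f = 2:

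| L | T = 0 | T = −30 |
|---|---|---|
| 60 | +12 | +18 |
| 40 | +8 | +14 |
| 20 | +4 | +10 |
| 0 | 0 | +6 |
| −15 | −3 | +3 |

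Against a no-reduction score, the upward shift needs a last area below baseline. At L = 0 it vanishes, and at L = −15 LOCF itself scores worsening.

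**Illustration 3: effect on the tests.** Eight assumed completers have reductions of 100, 80, 65, 50, 35, 20, 0 and −30 (mean 40, SD 42.8). Two failures are added; zeros are dropped for the Wilcoxon test.

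| Failures scored | Mean | 95% CI | t-test p | Wilcoxon p |
|---|---|---|---|---|
| 40 (LOCF) | 40.0 | 13.0 to 67.0 | 0.009 | 0.012 |
| 0 | 32.0 | 2.4 to 61.6 | 0.037 | 0.047 |
| −30 | 26.0 | −8.3 to 60.3 | 0.121 | 0.129 |

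The interval is 54.0 points wide under LOCF, 59.2 with a zero score and 68.6 with −30. Here the carried values equal the completers' mean, so they add subjects without adding spread.

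**When are later data missing?** The sections differ. On major surgery, section 7.1 says: "However, if major surgery is required, the subject should stop TWB-103 treatment". Section 6.7 says: "However, if major surgery is required, the subject should be withdrawn from this study". Serious wound infection is a reason to stop TWB-103 in sections 4.1 and 7.1, and a withdrawal ground in section 7.2. If these subjects only stop treatment and keep attending, Week 12 is observed and LOCF is not used. If they leave, it is.

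**The case against.** A reader might infer that LOCF scores every treatment failure as partial healing unless the exit visit is attended. The documents do not support that. The credit arises only if the last area was below baseline and was measured before the failure. Ulcer evaluation is scheduled at every weekly treatment visit (sections 1.3 and 8.3.3), so a failure found there can be measured and that area carried. The gap is a failure found between visits: at unscheduled visits, ulcer evaluation is at the investigator's decision (section 1.3, footnote 6; section 8.3.6).

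A reader might also infer that dropout after these events is certain. Section 7.2 says only that a subject may withdraw, and sections 4.1 and 7.1 speak of stopping treatment. The withdrawal route is nonetheless in the text, in sections 6.7 and 7.2.

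Other points on the plan's side stand:
- There is no formal hypothesis (section 9.1), efficacy is exploratory, and section 9.3 rests the main conclusion on the primary endpoint, which is safety. Wound infection and unexpected surgery are AEs singled out for discussion, so failures will not be hidden.
- Endpoints 3 and 6 are worded as individual reductions, and individual results would show a failed wound directly. Section 9.4.3 still adds group tests of area and volume.
- The closure endpoint is not affected: a wound last seen open stays open under LOCF, and section 8.1.1 does not count a wound as healed at a given week if a confirmation visit is missed.
- PP drops many of these subjects, through the 9-application minimum and the bar on prohibited treatment. That limits the LOCF problem mainly to ITT, though PP then has a selection problem instead.
- Section 9.4.3 does not say whether change is in percent or cm², so the percent figures may not be on the tested scale.
- The separate SAP may refine the rule, but LOCF is the only one stated.

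**Conclusion.** The point holds as a conditional one. LOCF without exception, together with withdrawal for wound-related failure and an optional exit assessment, allows pre-failure shrinkage to stand as the Week 12 result in the ITT area and volume tests. Where that happens, the mean reduction is biased upward.

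Under the first set of assumptions with 2 failures, LOCF with no exit visit exceeds a no-reduction score by 7 points (55 against 48) and a recorded post-failure area by 11 (55 against 44). In the assumed data set the scoring choice moves the result across 0.05. All sizes rest on assumed reductions and failure counts; no stated figure in the plan is shown to be wrong.

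The consequence is modest, because area and volume are exploratory secondary measures. It merits correction because the remedy is cheap and must be chosen before the data are seen.

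**What to change.** In section 9.4.1 and the SAP, before data lock, for ITT area and volume:

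1. After a wound-related withdrawal (section 7.2 items 6 and 8, and item 3 when the prohibited therapy was given for the study wound), score later weeks as no reduction from baseline, or as the largest observed area if that is above baseline.
2. Do not apply this score to withdrawals unrelated to the wound. Item 5 is a catch-all, item 7 is allergy, and item 3 can concern another condition; a zero score there could bias the mean downward.
3. Use areas actually observed wherever the subject continues to attend.
4. Keep LOCF as a sensitivity analysis.
5. Show observed and imputed counts at each week, beside individual profiles.

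Separately, reconcile sections 4.1 and 7.1 (stop treatment) with sections 6.7 and 7.2 (withdraw from the study), so that it is clear when later data are missing. Which clinical rule applies is for the sponsor and investigators to settle.

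The cost is SAP wording and one table. The reported mean reduction may be less favourable. The failure score is still single imputation, and it reduces but does not remove dependence on the exit visit: in the first illustration with 2 failures, the mean is 48 if the visit is skipped and 44 if it is attended. That is a gap of 4 points instead of 11.

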9.4.2 ANALYSIS OF THE PRIMARY ENDPOINT

Adverse events observed during the study will be coded using Medical Dictionary for Regulatory Activities (MedDRA) and will be reported by System/Organ/Class (SOC) classified in MedDRA as appropriate.

9.4.3 ANALYSIS OF THE SECONDARY ENDPOINTS

For changes of wound area and (if data available) wound volume measured by 3D camera from the baseline values, data will be analyzed by using one-sample t-test or Wilcoxon sign rank test on ITT and PP population.

9.4.4 SAFETY ANALYSES

Adverse events will be coded by employing MedDRA. Each AE will be counted once only for a given subject. Severity, frequency, and relationship of AEs to study intervention will be presented by System Organ Class (SOC) and preferred term groupings. The information of AEs, such as start date, stop date,

severity, relationship, outcome, and duration, should be reported. Serious treatment-emergent AE should be presented either in a table or a listing.

Changes in physical examinations will be displayed for each individual system. Net changes from pre-treatment laboratory test results and vital signs will be analyzed by descriptive statistics.

9.4.5 BASELINE DESCRIPTIVE STATISTICS

Demographics and baseline characteristics will be will be summarized by using descriptive statistics.

9.4.6 PLANNED INTERIM ANALYSES

Interim analyses are not planned for this study.

10 SUPPORTING DOCUMENTATION AND OPERATIONAL CONSIDERATIONS

10.1 REGULATORY, ETHICAL, AND STUDY OVERSIGHT CONSIDERATIONS

10.1.1 INFORMED CONSENT PROCESS

Consent forms describing in detail the study intervention, study procedures, and risks are given to the subject and written documentation of informed consent is required prior to starting intervention or administering study intervention. Different Informed Consent Forms (ICFs) subject to regulations and guidelines applicable to clinical studies of local countries and IRB/IEC requirements are submitted to regulatory authorities and IRBs/IECs, respectively, for approval.

In obtaining and documenting informed consent, the investigator must comply with regulations and guidelines applicable to clinical studies of local countries and IRB/IEC requirements and should adhere to International Conference on Harmonization Good Clinical Practice (ICH GCP). Prior to the beginning of the trial, the investigator should have the IRB/IEC's written approval for the protocol and the written informed consent form(s) and any other written information to be provided to the subjects. A separate screening consent will not be used for this study. The study consent must be signed prior to conducting study screening procedures.

Informed consent is a process that is initiated prior to the individual's agreeing to participate in the study and continues throughout the subject's study participation. Consent forms will be IRB/IEC-approved and the subject will be asked to read and review the document. The investigator will explain the study to the subject and answer any questions that may arise. A verbal explanation will be provided in terms suited to the subject's comprehension of the purposes, procedures, and potential risks of the study and of their rights as subjects. Subjects will have the opportunity to carefully review the written consent form and ask questions prior to signing. The subjects should have the opportunity to discuss the study with their family or surrogates or think about it prior to agreeing to participate. The subject will sign the informed consent document prior to any procedures being done specifically for the study. Subjects must be informed that participation is voluntary and that they may withdraw from the study at any time, without prejudice. A copy of the signed informed consent document will be given to the subjects for their records. The informed consent process will be conducted and documented in the source document (including the date) and the ICF will be signed before the subject undergoes any study-specific procedures. The rights and welfare of the subjects will be protected by emphasizing to them that the quality of their medical care will not be adversely affected if they decline to participate in this study.

10.1.2 STUDY DISCONTINUATION AND CLOSURE

This study may be temporarily suspended or prematurely terminated if there is sufficient reasonable cause. Written notification, documenting the reason for study suspension or termination, will be provided by the suspending or terminating party to subjects, investigator, the sponsor/CRO and regulatory authorities, whichever is applicable. If the study is prematurely terminated or suspended, the Principal Investigators (PIs) will promptly inform subjects, the IRB/IEC, and sponsor/ contract research organization (CRO), whichever is applicable and will provide the reason(s) for the termination or suspension. Subjects will be contacted, as applicable, and be informed of changes to study visit schedule.

Circumstances that may warrant termination or suspension include, but are not limited to:

- Determination of unexpected, significant, or unacceptable risk to subjects, i.e. ≥ 3 subjects received TWB-103 have developed grade 3 or above AEs according to CTCAE 5.0, independent of attribution. If the cause of AE can be identified and resolved, the study may be resumed.
- Demonstration of efficacy that would warrant stopping
- Insufficient compliance to protocol requirements
- Data that are not sufficiently complete and/or evaluable
- Determination that the primary endpoint has been met
- Determination of futility

The study may resume once concerns about safety, protocol compliance, and data quality are addressed, and satisfy the sponsor, IRBs/IECs and/or regulatory authorities.

10.1.3 CONFIDENTIALITY AND PRIVACY

Subject confidentiality and privacy is strictly held in trust by the participating investigators, their staff, and the sponsor/CRO. This confidentiality is extended to cover testing of biological samples and genetic tests in addition to the clinical information relating to subjects. Therefore, the study protocol, documentation, data, and all other information generated will be held in strict confidentiality. No information concerning the study or the data will be released to any unauthorized third party without prior written approval of the sponsor.

All activities will be conducted in as private a setting as possible.

The study monitor, other authorized representatives of the sponsor, representatives of the IRB/IEC, or regulatory authorities may inspect documents and records required to be maintained by the investigator, including but not limited to, medical records (office, clinic, or hospital) and pharmacy records for the subjects in this study. The clinical study site will permit access to such records.

The subject's contact information will be securely stored at each clinical site for internal use during the study. At the end of the study, all records will continue to be kept in a secure location for as long a period as dictated by the reviewing IRB/IEC, policies of regulatory authorities, or sponsor requirements.

Subject data, which is for purposes of statistical analysis and scientific reporting, will be transmitted to and stored at the responsible CRO. This will not include the subject's contact or identifying information. Rather, individual subjects and their data will be identified by a unique study identification number. The study data entry and study management systems used by clinical sites and by responsible CRO staff will be secured and password protected.

